6.18 ANALYSIS OF BREAKTHROUGH INFECTIONS

Table 15. Generic Estimand-to-Analysis table for all breakthrough infection endpoints for incidence risk (specified in Table 9).

(specified in Table 9).				
Primary Objective (as per Protocol): Identify any difference in the risk of clinically significant COVID-19 cases between any of the study groups [Indonesia Trial and BCOV22]; Evaluate the safety of the booster dose regimens [all studies]				
Estimand (for each trial vaccine):		Incidence risk of [OUTCOME]* to [TIMEPOINT]*, by dosage (fractional or standard) and trial vaccine in adults 18 years or older in Indonesia who have been primed through previous vaccination with one of the included primary series.		
ESTIMAND Attributes:		Incorporation of Estimand Attribute in ANALYSIS:		
Treatment Fractional dose (for each	trial vaccine)	Study arms Interventions (for each trial vaccine): Fractional dose Comparisons (for each trial vaccine): Standard dose		
Target population Adults 18 years or older in Indonesia/Mongolia who have been primed through previous vaccination with one of the included primary series.		Analysis set All randomised participants		
Variable		Outcome measure		
SARS-CoV-2 infection (bre		At least one positive SARS-CoV-2 test (PCR)		
Handling of intercurrent		Handling of missing data		
Receipt of 4 th dose (self-initiated)	Strategy ⁴ Treatment Policy (interpret results in conjunction with 4 th dose coverage)	Active surveillance for SARS-CoV-2 is not being done. Therefore, participants without a positive SARS-CoV-2 test will be included in the analysis under the assumption that they have not had a breakthrough infection.		
Receipt of 4 th dose (rescue) Treatment Policy (interpret results in conjunction with extent of rescue vaccination)				
Population-level summary measure		Analysis approach		
Incidence risk (proportion	n positive)	The incidence risk (a proportion) will be estimated in each group (arm [fractional or standard] and trial vaccine) with 95% CI using the proportion command in Stata. Analyses are descriptive only (no comparisons between arms will be made).		

^{*}This table is generic for all breakthrough infection endpoints for incidence risks (with varying combinations of outcomes & timepoints) specified in Table 9 as they will be analysed in the same way.

Table 16. Generic Estimand-to-Analysis table for all breakthrough infection endpoints for incidence rate (specified in Table 9).

(specified in Table 9).	Duetos N. Idontifu difference in the	a viele of clinically cignificant COVID 40		
Primary Objective (as per Protocol): Identify any difference in the risk of clinically significant COVID-19 cases between				
		the safety of the booster dose regimens [all studies]		
Estimand (for each trial vaccine):		Incidence rate of [OUTCOME]* to [TIMEPOINT]*, by		
		dosage (fractional or standard) and trial vaccine in		
		adults 18 years or older in Indonesia who have been		
		primed through previous vaccination with one of the		
		included primary series.		
ESTIMAND Attributes:		Incorporation of Estimand Attribute in ANALYSIS:		
Treatment		Study arms		
Fractional dose (for each tr	rial vaccine)	Interventions (for each trial vaccine): Fractional dose		
		Comparisons (for each trial vaccine): Standard dose		
Target population		Analysis set		
	Indonesia/Mongolia who have been	All randomised participants		
•	accination with one of the included			
primary series.	decination was one of the meladed			
Variable		Outcome measure		
SARS-CoV-2 infection (brea	kthrough infection)	Positive SARS-CoV-2 test (PCR) (multiple infections		
		within one participant are counted)		
Handling of intercurrent e	vents	Handling of missing data		
Event	Strategy ⁴	Active surveillance for SARS-CoV-2 is not being done.		
	Treatment Policy (interpret	Therefore, participants without a positive SARS-CoV-		
Receipt of 4th dose (self-	results in conjunction with 4 th	2 test will be included in the analysis as being		
initiated)	dose coverage)	negative. Participants lost to follow up will be		
- 4	Treatment Policy (interpret	censored at their last visit.		
Receipt of 4 th dose	results in conjunction with extent			
(rescue)	of rescue vaccination)			
Population-level summary		Analysis approach		
Incidence rate per 1000 pe		Participants will be considered at risk from Day 0 and		
mederice rate per 1000 pe	ison years	censored on the day of the last study visit that was		
		attended; participants will also be censored from the		
		day of a positive SARS-CoV-2 test but will re-enter		
		after 28 days. Failure will be a positive SARS-CoV-2		
		test, and multiple failures will be allowed in a single		
		•		
		participant. The incidence rate per 1000 person-		
		years will be estimated in each group (arm		
		[fractional or standard] and trial vaccine) with 95%		
		Cl using the strate command in Stata, after		
		declaring the data as survival data and specifying		
		person-time at risk and the failure variable using the		
		stset command. Analyses are descriptive only (no		
		comparisons between arms will be made).		

^{*}This table is generic for all breakthrough infection endpoints for incidence rates (with varying combinations of outcomes & timepoints) specified in Table 9 as they will be analysed in the same way.

7 PLANNED TABLES AND FIGURES

7.1 PLANNED TABLES AND FIGURES

Main		Dummy Table
Table 1	Summary of trial vaccines	Dummy Table 1
Figure 1	CONSORT diagram	Dummy Figure 1
Table 2	Baseline characteristics by third dose allocation	Dummy Table 2
Figure 2	Seroresponse rate at Day-28 between fractional and	Dummy Figure 2
	standard dose groups, by third dose vaccine allocation	
	(primary endpoint)	
Figure 3	Radial graph for solicited grade 3 or 4 local and systemic	Dummy Figure 3
	reactions within 7 days of boosting, inclusive, by third	
	dose allocation	
Table 3	Immune responses at Day-28 by third dose allocation	Dummy Table 3
Table 4	Immune responses at Month-6 by third dose allocation	Dummy Table 3
	and priming vaccine	
Table 5	Immune responses at Month-12 by third dose allocation	Dummy Table 3
	and priming vaccine	
Suppler	ment	
Table S1	Baseline characteristics by third dose allocation, stratified	Dummy Table 2,
	by primary series	split by primary
		series
Table S2	Proportion of participants who received a 4th dose during	Dummy Table S 1
	the study period	
Figure S1	Seroresponse rate at Day-28 between fractional and	Dummy Figure S 1
	standard dose groups, by third dose vaccine allocation	
	and primary series	
Figures S2	Radial graph for solicited grade 3 or 4 local and systemic	Dummy Figure S 2
	reactions within 7 days of boosting, inclusive, by third	
	dose allocation and primary series	
Figure S3	Distribution of [immunological parameter] at baseline	Box and whisker
	and Day-28 [and Month-6 and Month-12], by third dose	plot showing
	allocation and primary series	median, 25 th
		percentile, 75 th
		percentile, min
		and max. Repeat
		for each
		immunological
Eiguro CA	Percentage of individuals with each reaction and essentity	parameter. Dummy Figure S 3
Figure S4	Percentage of individuals with each reaction and severity grade, for each schedule.	Dullilly rigure 5.3
Table S3	Immune responses at Day-28 by third dose allocation and	Dummy Table S 2
14016 22	primary series	Duffiffy Table 3 2
Table S4	Frequency and outcomes of unsolicited adverse events	Dummy Table S 3
1able 54	and serious adverse events	Duffillity Table 5 5
	and serious adverse events	I

Figure S5	Frequency of unsolicited adverse events to Day 28	Dummy Figure S 4
	(inclusive) by SOC and severity	
Figure S6	Day of unsolicited AE onset (days post-booster) to Day 28	Dummy Figure S 5
	(inclusive) by SOC	
Table S5	Line list of all unsolicited adverse events	-
Text	Summary of protocol violations	-
Table S6	Clinical observations prior to trial vaccination	-
Table S7	Concomitant medications (regular medications at	-
	baseline)	

[figure not shown]
7.1.1 Dummy Tables and Figures – Main

Dummy Table 1. Summary of trial vaccines

Study Group	Generic vaccine name	Route	Dose				
Comirnaty® standard full dose							
Comirnaty® fractional dose	Pfizer-BioNTech (BNT162b2)	Intramuscular	15µg				
Add rov	Add rows for each trial vaccine & arm						

CONSORT 2010 Flow Diagram

[figure not shown]

Dummy Figure 1. CONSORT Flow Diagram

[figure not shown]
Dummy Table 2. Baseline characteristics by third dose allocation

	Total (N = n)	Standard Dose (N = n)	Fractional Dose (N = n)	Additional
Age, years	Mean [SD] or Median {IQR}, min-max	(N = n) Mean (SD) or Median (IQR), min-max	Mean [SD] or Median {IQR}, min-max	columns will be
Age groups, years				Spikevax® and
<50	N (%)	N (%)	N (%)	Vaxzevria®
≥50	N (%)	N (%)	N (%)	groups in
Gender				Indonesia
Female	N (%)	N (%)	N (%)	
Male	N (%)	N (%)	N (%)	
Interval between 1st and 2nd dose, days	Median {IQR}, min-max	Median {IQR}, min-max	Median {IQR}, min-max	
Interval between 2 nd and 3 rd	Median (IQR), min-max	Median (IQR), min-max	Median (IQR), min-max	

dose, days			
Reaction to primary series	N (%)	N (%)	N (%)
Highest level of medical care			
sought for reaction to	N (%)	N (%)	N (%)
primary series			
No care/advice sought	N (%)	N (%)	N (%)
Pharmacy	N (%)	N (%)	N (%)
GP	N (%)	N (%)	N (%)
Emergency Department	N (%)	N (%)	N (%)
Admitted to Hospital	N (%)	N (%)	N (%)
Other	N (%)	N (%)	N (%)
Comorbidities	N (%)	N (%)	N (%)
Diabetes mellitus	N (%)	N (%)	N (%)
Gestational diabetes	N (%)	N (%)	N (%)
Cardiovascular disease	N (%)	N (%)	N (%)
Hypertension	N (%)	N (%)	N (%)
Cancer	N (%)	N (%)	N (%)
Chronic obstructive	N (0/)	N (0/)	N (0/)
pulmonary	N (%)	N (%)	N (%)
Chronic kidney disease	N (%)	N (%)	N (%)
Chronic liver disease	N (%)	N (%)	N (%)
Anaphylaxis (or carries an	N/0/\	N/0/)	N (0/)
EpiPen)	N (%)	N (%)	N (%)
Neurological disease	N/9/\	N/0/\	N/0/1
(including stroke)	N (%)	N (%)	N (%)
Anticoagulant therapy	N (%)	N (%)	N (%)
Immunocompromised	N (%)	N (%)	N (%)
Mastocytosis causing	N (%)	N/9/\	N (9/)
recurrent anaphylaxis	N (76)	N (%)	N (%)
Cigarette user	N (%)	N (%)	N (%)
Currently pregnant	N (%)	N (%)	N (%)

Dummy Figure 2. Seroresponse rate at Day-28 between fractional and standard dose groups (primary endpoint), by trial vaccine

Dummy Figure 3. Radial graph for solicited grade 3 or 4 local and systemic reactions within 7 days of boosting, inclusive, by trial vaccine [there will be one radial graph for each trial vaccine – i.e. 3 in Indonesia and 1 in Mongolia]

Dummy Table 3. Immune responses at << Day-28/Month-6/Month-12>> by third dose allocation

	Boost wit		
	Standard (N = n) Fractional (N = n)		
Binding Antibodi	es (IgG), BAU/mL		
GMT (95% CI)	xxx (xxx-xxx; n=xx)	xxx (xxx-xxx; n=xx)	Additional columns
GMR (95% CI)	Ref x.xx (x.xx-x.xx)		will be added for
ACE2 Binding* in	hibition by neutralising antibody (wi	ld type), %	Spikevax® and
Mean	xx (xx-xx; n=xx)	xx (xx-xx; n=xx)	Vaxzevria® groups in
MD	Ref	x (x-x)	Indonesia
ACE2 Binding* in			

[figure not shown]
	, .	, .
Mean	xx (xx-xx; n=xx)	xx (xx-xx; n=xx)
MD	Ref	x (x-x)
Neutralising antil	oody (wild type), NT50	
GMT (95% CI)	xxx (xxx-xxx; n=xx)	xxx (xxx-xxx; n=xx)
GMR (95% CI)	Ref	x.xx
	Nei	(x.xx-x.xx)
Neutralising antil	oody (Delta), NT ₅₀	
GMT (95% CI)	xxx (xxx-xxx; n=xx)	xxx (xxx-xxx; n=xx)
GMR (95% CI)	Ref	x.xx (x.xx-x.xx)
Neutralising antil	oody (Omicron), NT ₅₀	
GMT (95% CI)	xxx (xxx-xxx; n=xx)	xxx (xxx-xxx; n=xx)
GMR (95% CI)	Ref	x.xx (x.xx-x.xx)
IFNγ, IU/ml		
GMT (95% CI)	xxx (xxx-xxx; n=xx)	xxx (xxx-xxx; n=xx)
GMR (95% CI)	Ref	x.xx (x.xx-x.xx)
IFNγ-producing co	ells, cells/million PBMCs	
GM (95% CI)	xxx (xxx-xxx; n=xx)	xxx (xxx-xxx; n=xx)
GMR (95% CI)	Ref	x.xx (x.xx-x.xx)

GMT: Geometric mean titre; GMR: geometric mean ratio; GM: geometric mean; MD: difference in means; Ref: Reference group. *Inhibition of binding between the SARS-CoV-2 receptor binding domain and the host-cell ACE2 receptor by neutralising antibody.

7.1.2 Dummy Tables and Figures - Supplement

[figure not shown]
Dummy Table S 1. Proportion of participants who received a 4th dose during the study period

		Prime with Vaxzevria®				Prime with Comimaty®			
	Boos	Boost with		Boost with		Boost with		Boost with	
	Comi	Comimaty®		Spikevax®		Comirnaty®		Spikevax®	
	Standard	Fractional	Standard	Fractional	Standard	Fractional	Standard	Fractional	
	(N = n)	(N = n)	(N = n)	(N = n)	(N = n)	(N = n)	(N = n)	(N = n)	
Received 4 th dose	N (%)	N (%)	N (%)	N (%)	N (%)	N (%)	N (%)	N (%)	
Before Month-6	N (%)	N (%)	N (%)	N (%)	N (%)	N (%)	N (%)	N (%)	
visit, self-initiated									
Before Month-6	-	N (%)	-	N (%)	-	N (%)	-	N (%)	
visit, as rescue									
After Month-6 visit,	N (%)	N (%)	N (%)	N (%)	N (%)	N (%)	N (%)	N (%)	
self-initiated									

[figure not shown]

ld: lower confidence interval; ud: upper confidence interval; Dotted vertical line is the non-inferiority margin

Dummy Figure S 1. Seroresponse rate at Day-28 between fractional and standard dose groups, by trial vaccine and primary series

Dummy Figure S 2. Radial graph for solicited grade 3 or 4 local and systemic reactions within 7 days of boosting, inclusive, by trial vaccine and primary series

Dummy Figure S 3. Dummy figure to show the percentage of individuals with each reaction and severity grade, for each schedule.

Dummy Table S 2. Immune responses at <<Day-28/Month-6/Month-12>> by third dose allocation and primary series

	Boost	with X®	Boost with Y®					
	Standard (N = n)	Fractional (N = n)	Standard (N = n)	Fractional (N = n)	Additional columns will be			
Binding Antib	added for all							
GMT (95% CI)	xxx (xxx-xxx; n=xx)	xxx (xxx-xxx; n=xx)	xxx (xxx-xxx; n=xx)	xxx (xxx-xxx; n=xx)	unique combinations of			
GMR (95% CI)	Ref	x.xx (x.xx-x.xx)	Ref	x.xx (x.xx-x.xx)	primary series and trial vaccine			
ACE2 Binding								
Mean	xx (xx-xx; n=xx)	xx (xx-xx; n=xx)	xx (xx-xx; n=xx)	xx (xx-xx; n=xx)				
MD	Ref x (x-x)		Ref	x (x-x)				
ACE2 Binding								
Mean	xx (xx-xx; n=xx)	xx (xx-xx; n=xx)	xx (xx-xx; n=xx)	xx (xx-xx; n=xx)				
MD	Ref	x (x-x)	Ref	x (x-x)				
Neutralising	Neutralising antibody (wild type), NT ₅₀							
GMT (95% CI)	ххх (ххх-ххх; n=xx)	жх (ххх-ххх; n=ж)	xxx (xxx-xxx; n=xx)	xxx (xxx-xxx; n=xx)				
GMR	Ref	x.xx	Ref	x.xx				

(95% CI)		(x.xx-x.xx)		(x.xx-xx.x)				
Neutralising antibody (Delta), NT ₅₀								
GMT (95% CI)	xxx (xxx-xxx; n=xx)	κκ (xxx-xxx; n=κκ)	xxx (xxx-xxx; n=xx)	xxx (xxx-xxx; n=xx)				
GMR (95% CI)	Ref	x.xx (x.xx-x.xx)	Ref	x.xx (x.xx-x.xx)				
Neutralising antibody (Omicron), NT ₅₀								
GMT (95% CI)	xxx (xxx-xxx; n=xx)	xxx (xxx-xxx; n=xx)	xxx (xxx-xxx; n=xx)	xxx (xxx-xxx; n=xx)				
GMR (95% CI)	Ref	x.xx (x.xx-x.xx)	Ref	x.xx (x.xx-x.xx)				
IFNγ, IU/ml								
GMT (95% CI)	xxx (xxx-xxx; n=xx)	xxx (xxx-xxx; n=xx)	xxx (xxx-xxx; n=xx)	xxx (xxx-xxx; n=xx)				
GMR (95% CI)	Ref	x.xx (x.xx-x.xx)	Ref	x.xx (x.xx-x.xx)				
IFNγ-producing cells, cells/million PBMCs								
GM (95% CI)	xxx (xxx-xxx; n=xx)	νοιχ (xxx-xxx; n=να)	xxx (xxx-xxx; n=xx)	xxx (xxx-xxx; n=xx)				
GMR (95% CI)	Ref	x.xx (x.xx-x.xx)	Ref	x.xx (x.xx-x.xx)				

[figure not shown]
GMT: Geometric mean titre; GMR: geometric mean ratio; GM: geometric mean; MD: difference in means; Ref: Reference group. *Inhibition of binding between the SARS-CoV-2 receptor binding domain and the host-cell ACE2 receptor by neutralising antibody.

Dummy Table S 3. Frequency and outcomes of unsolicited adverse events and serious adverse events

[figure not shown]
	Boost with Comirnaty®			
	Total	Standard	Fractional	1
	(N = n)	(N = n)	(N = n)	Additional columns will be ad
Any AE to Day 28 (inclusive) *	N (%)	N (%)	N (%)	Spikevax® and Vaxzevria® gr
Any Grade 3 - 5 AE to Day 28 (inclusive)*^	N (%)	N (%)	N (%)	Indonesia
AE Outcome#				
Resolved	N (%)	N (%)	N (%)	
Resolved with sequelae	N (%)	N (%)	N (%)	
Ongoing	N (%)	N (%)	N (%)	
Fatal	N (%)	N (%)	N (%)	
Unknown	N (%)	N (%)	N (%)	
Medically attended AE to Month- 3 visit (inclusive)	N (%)	N (%)	N (%)	
Any SAE to study-end ^a				
SOC A	N (%)	N (%)	N (%)	
SOC B	N (%)	N (%)	N (%)	
SOC C	N (%)	N (%)	N (%)	
for all SOCs	N (%)	N (%)	N (%)	
SAE Outcome#				
Resolved	N (%)	N (%)	N (%)	
Resolved with sequelae	N (%)	N (%)	N (%)	
Ongoing	N (%)	N (%)	N (%)	
Fatal	N (%)	N (%)	N (%)	
Unknown	N (%)	N (%)	N (%)	

^{*}Unsolicited Adverse events within 28 days inclusive will be considered, rather than all adverse events prior to the Day-28 visit, which can occur between 28- and 35-days post-booster. 'Recurrent events in the same individual will be

counted as a single event (using information from the most severe occurrence); all recurrences will be included in the line list of all adverse events. "Denominator is the total number of AEs/SAEs rather than the number of participants.

Dummy Figure S 4. Frequency of unsolicited adverse events to Day 28 (inclusive) by SOC and severity, and event duration. A – G are different SOCs. Colours represent event severity (Blue=Mild; Red = Severe). [Note: This type of figure will be generated separately for each trial vaccine and presented in panels within a single figure.]

Dummy Figure S 5. Onset (days post-booster) of unsolicited AE to Day 28 (inclusive) by SOC. Dummy figure is from Phillips *et al.* 2022.⁷ X-axis will be the day of onset rather than the number of adverse events. Mepolizumab and Placebo correspond to Fractional and Standard Dose groups. [Note: This type of figure will be generated separately for each trial vaccine and SOC and presented in panels within a single figure.]

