4.2 REACTOGENICITY AND SAFETY OUTCOMES

Table 4 summarises the reactogenicity and safety outcomes and relevant parameters. Further details on all collected parameters are stored in RedCAP Codebooks, as detailed in the Data Management Plan. Definitions of the terms adverse event, adverse reaction, and serious adverse event are given in the Protocols, and are aligned with definitions used in trials involving investigational medicinal products.

Table 4. Reactogenicity and safety outcomes

Outcome	Parameter	Categories	Timepoints	
	Pain			
	Tenderness			
	Redness	Grade 0, 1, 2, 3, or		
	Swelling	4*		
Reactogenicity (local)	Hardness] 4		
	Axillary			
	lymphadenopathy			
	Warmth	Binary	Day 1, 2, 3, 4, 5, 6, &	
	Itch	(presence/absence)	7	
	Fever			
	Nausea			
	Vomiting	Grade 0, 1, 2, 3, or		
Reactogenicity (general/systemic)	Diarrhoea	4*		
	Headache	4		
	Fatigue/Malaise			
	Myalgia			

	Arthralgia			
	Experienced an adverse event	Binary (yes/no)		
	System Organ Class [^]	As per MedDRA		
	Severity	Severity Grade 1 (mild), 2 (moderate), 3 (severe), 4 (life- threatening), 5 (fatal)#	Adverse Events to 28 Days: Day-0, -1, -7, and -28 visits, and	
Adverse Events to 28 Days Adverse Reaction to 28 Days ⁸ Serious Adverse Events to 12 months	Outcome	1-Resolved 2-Resolved with sequelae 3-Ongoing 4-Fatal 5-Unknown	Month-3 visit (for new information, e.g., resolution) Serious Adverse Events to 12 months:	
	Serious	Binary (yes/no)	Unscheduled (participants instructed to contact	
	Onset (days from trial vaccination)	Continuous	study staff)	
	Event duration (days)	Continuous	study starry	
	Relatedness	1-Unrelated 2-Possible 3-Probable 4-Definite		

^{*5-}point severity scale: 0-None; 1-Mild; 2-Moderate; 3-Severe; 4-Life-threatening. Refer to Protocol for more detailed definitions. Grading for hardness and swelling in Mongolia will not consider interference with daily activities as per the protocol as this information is not being captured. #Grade 3-4 events may be SAEs; all Grade 5 events are automatically considered as SAEs. ^Will require derivation from 'event_term' and 'saefin' fields by study team. ⁸An adverse reaction is an adverse event with causality assessment of either Possible, Probable, or Definite.

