5.3 SAFETY ENDPOINTS

Table 8. Safety endpoints

Safety Endpoint	Outcome	Timepoint	Population measure	Comparison	Measure of association
i.	Any# AE to Day 28 (inclusive)*	28 days post- booster	Frequency [N (%)]	Fractional vs. Standard	Descriptive only
ii.	Any# AE to Day 28 (inclusive)* ^ by severity	28 days post- booster	Frequency [N (%)]	Fractional vs. Standard	Descriptive only
iii.	Any# AE to Day 28 (inclusive)* ^ by causality assessment	28 days post- booster	Frequency [N (%)]	Fractional vs. Standard	Descriptive only
iv.	Any AE to Day 28 (inclusive)* by SOC and severity^	28 days post- booster	Frequency [N (%)]	Fractional vs. Standard	Descriptive only
v.	Duration# of AE to Day 28 (inclusive)* by SOC^	28 days post- booster	Median days {25 th – 75 th percentile}, min - max	Fractional vs. Standard	Descriptive only
vi.	Day of AE onset (days post-booster) to Day 28 (inclusive)* by SOC^	28 days post- booster	N by Day	Fractional vs. Standard	Descriptive only
vii.	AE to Day 28 (inclusive)* by Outcome**^	28 days post- booster	Frequency [N (%)]	Fractional vs. Standard	Descriptive only
viii.	Medically attended unsolicited AE to Month-3 visit (inclusive)	90 days post- booster	Frequency [N (%)]	Fractional vs. Standard	Descriptive only
ix.	SAE to study-end by SOC and expectedness ^a	Month-12 visit	Frequency [N (%)]	Fractional vs. Standard	Descriptive only
x.	SAE to study-end by Outcome**^	Month-12 visit	Frequency [N (%)]	Fractional vs. Standard	Descriptive only

[&]quot;The Safety analysis will only include unsolicited adverse events; solicited adverse events are considered in the Reactogenicity analysis. "Adverse events within 28 days inclusive will be considered, rather than all adverse events prior to the Day-28 visit, which can occur between 28- and 35-days post-booster. "Outcome categories are Resolved, Resolved with sequelae, Ongoing, Fatal and Unknown; denominator is the total number of SAEs rather than the number of participants. 'Recurrent events in the same individual will be counted as a single event (using information from the most severe occurrence); all recurrences will be included in the line list of all adverse events. "Event duration of 'Ongoing' adverse events will be the number of days between onset and the last visit.

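### SAP Table 8 sets the number of SAEs as the denominator for AE outcomes, and no planned row reports participants with any SAE, or participants who died, by dose to study end

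*SAP*

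**What the plan says.** **Table 8 (SAP 5.3).** Two rows classify events by how they ended: row vii, "AE to Day 28 (inclusive)* by Outcome", and row x, "SAE to study-end by Outcome". One footnote lists the outcome categories and then says "denominator is the total number of SAEs rather than the number of participants". The remaining SAE endpoint is row ix, "SAE to study-end by SOC and expectedness". All these rows are N (%), presented as fractional versus standard and labelled descriptive. Study end for SAEs is the Month-12 visit.

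**Dummy Table S 3 (SAP 7.1.2).** The AE outcome and SAE outcome blocks carry a different rule: "Denominator is the total number of AEs/SAEs rather than the number of participants". The line "Any SAE to study-end" has no N (%) of its own; the cells stand on the SOC rows beneath it. The rows for any AE, Grade 3 to 5 AEs, medically attended AEs and SAEs by SOC do not carry the event denominator.

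**Section 6.17.** Safety analyses use all randomised participants according to the vaccine received, reported separately by dose. Recurrences in one person count once, at the most severe occurrence. A line list by dose allocation gives patient identifier, seriousness and outcome for every adverse event.

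**The concern.** There are two problems.

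First, the SAP gives two denominators for the same AE outcome rows. The one in the endpoint table cannot be right for row vii, because most unsolicited AEs are not SAEs and the two counts need not even cover the same period. An analyst following Table 8 gets impossible percentages; an analyst following Dummy Table S 3 departs from the endpoint definition.

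Second, any AE and medically attended AEs each have an overall row (Table 8, rows i and viii), but SAEs do not. They appear only split by SOC and expectedness, or by outcome per event. A reader who wants to know what proportion of each dose group had a serious event, or died, will not find it in a planned row. The percentage that is offered beside fatal outcomes uses the number of events as its base. That number is itself a post-vaccination result in each arm, so the percentage does not measure risk per randomised participant. Safety of the booster regimens is a stated secondary objective, and these descriptive tables are the planned output for it.

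**Working it through.** The documents give no AE or SAE counts, so there is no figure of the plan's to reproduce. All counts below are assumed, for illustration. The one input taken from the documents is 400 participants per arm (SAP 3.3).

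**1. Row vii under each rule.** Assume one arm has 60 AEs to Day 28, of which 55 resolved, and 8 SAEs.

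| Rule | Resolved | All outcome rows together |
|---|---|---|
| Dummy Table S 3 (AEs) | 55/60 = 91.7% | 60/60 = 100% |
| Table 8 footnote (SAEs) | 55/8 = 687.5% | 60/8 = 750% |

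With no SAEs, the Table 8 percentage is undefined. For row x the two rules agree.

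**2. What a percentage per event measures.** For fatal outcomes,

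fatal share of SAEs = (fatal events / N) ÷ (SAEs / N).

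It is a ratio of two quantities that can each differ between arms. Assume one SAE per affected participant and N = 400.

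| Assumed arm | Fatal / SAEs | Fatal per participant (95% Clopper-Pearson CI) | Any SAE per participant (95% CI) |
|---|---|---|---|
| Standard | 2/8 = 25% | 2/400 = 0.5% (0.06 to 1.79) | 8/400 = 2.0% (0.87 to 3.90) |
| Fractional | 4/16 = 25% | 4/400 = 1.0% (0.27 to 2.54) | 16/400 = 4.0% (2.30 to 6.41) |

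Check: 0.5/2.0 = 1.0/4.0 = 25%. The event percentages are equal while both participant percentages double.

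The reverse can also occur. With 2 fatal of 12 SAEs in one arm and 2 of 6 in the other, the fatal shares are 16.7% and 33.3%, while 2/400 = 0.5% of participants died in each arm.

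**3. Whether the SOC rows give the missing count.** Assume SAE rows for three SOCs of 4, 3 and 2 participants. If the participants overlap fully, 4 people had an SAE; if not at all, 4 + 3 + 2 = 9. The proportion lies between 4/400 = 1.0% and 9/400 = 2.25%. The rows bound the number but do not state it.

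**4. Whether another row gives it.** The Grade 3 to 5 row stops at Day 28, while SAEs run to the Month-12 visit. Grade is also not seriousness: SAP Table 4 says "all Grade 5 events are automatically considered as SAEs", but that Grade 3 and 4 events may or may not be. Section 6.17 provides a line list from which the count can be made, but no row that states it.

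**The case against.** The strongest reply is that little is hidden. The event denominator attaches only to the outcome blocks. The other rows, including SAEs by SOC, appear to be participant-based under arm columns headed with N. The fatal row shows a count as well as a percentage, so equal deaths in two arms of 400 would be visible as equal. The recurrence rule limits multiple counting. The line list in section 6.17 lets anyone count participants with an SAE or a fatal event by dose, and section 6.1.8 allows extra descriptive statistics in the study report. An event denominator is also a defensible way to describe how events ended, and no between-arm test is planned on it.

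Most of this stands, and it sets the limits of the point. A reader might infer that risk of serious or fatal harm per participant cannot be recovered by dose. The documents do not support that: fatal counts beside the arm N give it if each death has one fatal event, and the line list gives the rest. A reader might also infer that the arm with more SAEs must show a smaller fatal share. That is not so: in the first example above SAEs double and the share is unchanged.

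The reply does not remove two things. The Table 8 footnote is wrong for row vii, even though Dummy Table S 3 already has a workable rule and an analyst would probably notice. And permission to add statistics, or a listing to count from by hand, is not a planned summary.

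**Conclusion.** The point holds as an error in a stated denominator and a gap in planned reporting; it is not a loss of data. Row vii of Table 8 cannot be computed sensibly as written and must be reconciled with Dummy Table S 3. No planned endpoint or filled table row reports participants with at least one SAE, or participants who died, by dose to study end, and the outcome percentages per event are no substitute. It should be corrected before the safety tables are produced, but it does not affect the primary analysis.

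The size cannot be estimated from the documents, because they give no event counts; the examples show only what the rules can do.

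The conclusion rests on two readings of the text. The footnote symbols are not all legible, so the link between rows vii and x and the denominator footnote is inferred from its opening list of outcome categories and from those being the only two rows by outcome. The Dummy Table S 3 line mentioning all SOCs is read as an instruction to repeat the SOC rows; if it were a total, it would partly supply the missing SAE count, and the SAP should say so.

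**What to change.** 1. In Table 8, change the outcome footnote so that row vii uses the arm's number of unsolicited AEs to Day 28 and row x uses the arm's number of SAEs to study end. Use the same wording in Dummy Table S 3.
2. Add two rows to Table 8 and to Dummy Table S 3, by dose to study end: participants with at least one SAE, and participants who died. Give each as n/N (%) of the arm's Safety Population.
3. Keep the event-based outcome percentages if wanted, labelled as a description of how reported events ended and not as risk by arm.

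The cost is a footnote correction and two table rows, from data already collected. The only downside is a slightly longer safety table.
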